*** Will you be recruiting individuals for participation in this study?**

Yes No

1. * Describe who will be recruiting individuals for participation for this study:

Study team members also involved in clinical care.

2. * Select all methods to be used for recruitment:

Directly approaching potential subjects (in-person)

3. * Provide details on your recruitment methods:

Individuals will be identified during the course of usual clinical care of patients at the University of Pittsburgh Voice Center. As potential subjects are being clinically evaluated in the University of Pittsburgh Voice Center, they will encounter at least one member of the research team who will be able to determine eligibility through the clinical review of medical records associated with their visit. Once verification of eligibility is obtained, potential subjects will be approached by a member of the research team to review the informed consent document. Any and all questions will be addressed during this time.

4. * Describe all compensation/incentives offered to participants and timing of these offers:

Participants will be paid \$100 in total for completion of the 4 voice therapy sessions and follow-up session. The \$100 payment will be made after the completion of the 5 visits (4 therapy and 1 follow up). There will be no partial payment. Payment will be managed with a reloadable debit card.

Participants will be paid when they present for the follow-up visit after completing 4 voice therapy sessions.

5. Recruitment materials: (attach all material to be seen or heard by subjects, including advertisements and scripts)

Document Category Date Modified Document History

There are no items to display

Study Aims

1. * Describe the purpose, specific aims, or objectives and state the hypotheses to be tested:

To determine the efficacy of a semi-occluded mask in the treatment of patients with voice disorders

To determine initial efficacy of a semi-occluded facemask on voice outcomes in patients with MTD, lesions, and atrophy. We hypothesize that patients will demonstrate an improvement in acoustic, aerodynamic outcomes, and voice handicap index scores following therapy.

2. * Describe the relevant prior experience and gaps in current knowledge including preliminary data. Provide for the scientific or scholarly background for, rationale for, and significance of the research based on existing literature and how it will add to existing knowledge:

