Our group recently developed a semi-occluded facemask for use in patients with and without voice disorders. Recent preliminary results using this semi-occluded facemask indicated that the use of a certain mask port diameters may elicit voice with increased efficiency. A study of 5 participants without voice disorders revealed that a mask occlusion diameter of 6.4 and 3.2 mm resulted in improved vocal efficiency. A study of the immediate effects of a semi-occluded facemask in 20 patients with voice disorders revealed that occlusions diameters of 9.6, 6.4, and 3.2 mm all resulted in significant improvements in acoustic and aerodynamic voice outcomes.

The current study aims to expand upon these past studies by investigating the efficacy of use of a semi-occluded facemask in the treatment of patients with voice disorders.

Study Design

1. **Total number of subjects to be enrolled at this site (enter -1 for chart reviews, banking, registries):**

30

2. **Describe and explain the study design:**

Prospective, experimental

3. **Describe the primary and secondary study endpoints:**

4. **Provide a description of the following study timelines:**

Duration of an individual subject's active participation:

Approximately 6 weeks

Duration anticipated to enroll all subjects:

12-18 months

Estimated date for the investigator to complete this study (complete primary analyses):

12/31/2019

5. **List the inclusion criteria:**

males and females

age 18-60 years old

diagnosed by a multi-disciplinary team consisting of laryngologist and speech-language pathologist with muscle tension dysphonia (MTD) or vocal fold lesions deemed amenable to voice therapy (i.e. not surgical candidates)

6. **List the exclusion criteria:**

Age 61 or older (excluded due to differences in vocal fold tissue structure changes in this age and older)

Under 18 years of age

Current smoker (greater than 5 cigarettes/week)

7. **Will children or any gender, racial or ethnic subgroups be explicitly excluded from participation?**

Yes No

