For all exercises, instruct patient to:

- Breathe outside of mask, phonate into mask
- Abdominal breathing
- Relaxed upper body
- SOMask connected speech- topic of subject's choice
- Auditory and kinesthetic awareness of voice production
- Embedded basic training gesture
- Prosody training
- Negative practice- patient produces the "good" voice, alternating with the "bad" voice

Home program:

- 1 min of mask speech, 4x/day practice
- Record sessions on patient's smart phone for home practice
- Log sheet for homework practice

Baseline data to be collected will be extracted from the medical record.

Data collected at Baseline:

- VHI-10 (per usual clinical care)
- auditory perceptual analysis (per usual clinical care)
- Acoustic outcomes in vowels and speech- "we were away a year ago" (per usual clinical care)
- Aerodynamic outcomes (per usual clinical care)

Medical record information will be accessed to collect clinical information related to eligibility for this project, and to record voice outcome measure information (such as the VHI-10). This information will be collected by individuals involved in this research who have normal clinical access to this information or by the research coordinator who has been granted access through the Privacy Office.

All recruitment and enrollment will take place at UPMC Mercy. Voice therapy sessions will occur at Mercy, East, and Passavant and Bethel Park.

Data collected at follow-up:

- VHI-10
- auditory perceptual analysis
- Acoustic outcomes in vowels and speech- "we were away a year ago"
- Aerodynamic outcomes
- Patient perception of voice therapy questionnaire
- Exit interview about voice therapy

2. Upload a copy of all materials used to collect data about subjects: (Attach all surveys, interview/focus group scripts, and data collection forms except for case report forms, SCID or KSADS):

Document	Category	Date Modified	Document History
View Patient Perception of Voice Therapy Ziegler_2014.pdf(0.01)	Data Collection	1/16/2019	History
View Dev and Valid of VHI-10 Rosen_et_al-2004-The_Laryngoscope.pdf(0.01)	Data Collection	1/16/2019	History

3. * Will blood samples be obtained for research purposes?

Yes No

Consent Process

Enter N/A in response to the following questions if a Waiver of Consent is requested for all research activities or if no subjects are being enrolled.

1. * Indicate where the consent process will take place and at what point consent will be obtained:

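### The before-after perceptual rating compares a chart score from routine care with a research-visit score for which no rater, scale, mode or masking is stated

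*Combined protocol and SAP*

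**What the plan says.** All references are to the Combined protocol and SAP.

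- **Baseline rating.** Research Activities, item 1, lists "auditory perceptual analysis (per usual clinical care") among the baseline measures and states: "Baseline data to be collected will be extracted from the medical record".
- **Follow-up rating.** Under "Data collected at follow-up" the same measure appears by name only, without the usual-care label. Follow-up is a research testing visit one week after four therapy sessions.
- **Who handles the data.** The same item says of the medical-record information: "This information will be collected by individuals involved in this research who have normal clinical access to this information", or by the research coordinator. This concerns collection. It does not say who makes a perceptual rating.
- **Voice samples.** "Acoustic outcomes in vowels and speech" are listed at both time points, with one standard sentence. The only recording described outright serves another purpose: "Record sessions on patient's smart phone for home practice".
- **Link to the device.** Study Aims, item 2: "Our group recently developed a semi-occluded facemask for use in patients with and without voice disorders".
- **Role of the measure.** The hypothesis (Study Aims, item 1) names acoustic, aerodynamic and voice handicap outcomes. The only stated test (Study Design, item 8) is a paired t-test on VHI-10. The endpoint item (Study Design, item 3) carries no text.

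**The concern.** Auditory-perceptual analysis is the one measure in the list that depends on a listener's judgement, so it is the one most open to what the listener expects. The two scores being compared also come from different processes: one from routine clinic work before therapy, the other from a research visit after it. Two sources of error can therefore look like a treatment effect. A rater who knows that a sample is post-treatment may score it more favourably. A different rater, or a different scale, may also score it systematically higher or lower.

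The study describes no control group, so nothing offsets either shift. The investigators developed the mask, and in the Risk and Benefits section they state the hypothesis that every participant will gain. Expectation is therefore a realistic concern.

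At stake is whether a perceptual improvement could be read as a listener's corroboration of the patient-reported VHI-10.

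**Working it through.** The plan gives no figure for this measure, so there is none to reproduce. The first part sets the passages side by side. The second is an illustration on assumed values.

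**1. What can be established about each rating**

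| Feature | Baseline | Follow-up |
|---|---|---|
| Source | Medical record, usual care | Research visit |
| Timing known to the rater | Yes: a clinic rating, with consent sought before any therapy (Consent Process, item 1) | Not stated |
| Rater | Not stated | Not stated |
| Scale | Not stated | Not stated |
| Live or from a recording | Not stated | Not stated |
| Masking | None possible within the study: the score already exists in the chart | Not stated |

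Masking only the follow-up rating would not repair the comparison. The baseline score is fixed in the chart and was made at a known pre-treatment time. A comparison masked on both sides needs both samples rated afresh under the same conditions.

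**2. Whether material for masked rating exists**

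Acoustic measures on vowels and a set sentence are planned at both time points, and such measures require captured audio. No section says that the audio is kept. The phone recordings are of therapy sessions for home practice and do not serve this purpose. Masked rating is therefore feasible if the audio is retained, and the plan needs to say that it will be.

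**3. Illustration of size (assumed values)**

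Inputs: n = 30 (Study Design, item 1) and n = 20 (Study Design, item 8). Assumed: a two-sided 5% paired t-test on the perceptual change score, no true change, and a systematic rater shift b of 0.10, 0.25 or 0.50 SD of the change score.

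Under these assumptions the test statistic has a noncentral t distribution with n − 1 degrees of freedom and noncentrality b × √n. The chance of a significant result is P(|T| > critical value), with critical values 2.093 (19 df) and 2.045 (29 df).

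| Shift b (SD) | b√20 | n = 20 | b√30 | n = 30 |
|---|---|---|---|---|
| 0 | 0 | 5.0% | 0 | 5.0% |
| 0.10 | 0.447 | 7.1% | 0.548 | 8.3% |
| 0.25 | 1.118 | 18.6% | 1.369 | 26.3% |
| 0.50 | 2.236 | 56.5% | 2.739 | 75.4% |

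The same percentages would follow for any outcome subject to the same shift. They show how sensitive a before-after test is to a rater shift. They are not evidence that a shift of any given size occurs in this trial.

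**4. Rating workload**

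Two clips per participant gives 2 × 20 = 40 to 2 × 30 = 60 clips. At an assumed 1.5 to 2 minutes each, that is 40 × 1.5 = 60 minutes to 60 × 2 = 120 minutes, or about 1 to 2 hours.

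**The case against.** The strongest reply is that the plan is silent rather than wrong, and that the measure is peripheral.

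- **Live, unmasked rating.** A reader might infer that the ratings are made live at each visit with the time point known. The documents do not say so. A known time point follows for baseline, but the follow-up entry states neither mode nor masking. This part of the objection stands.
- **Treating staff as raters.** A reader might infer that those who deliver the mask therapy also rate it. The statement "Study team members also involved in clinical care" answers who recruits, and the statement about developing the mask does not identify raters. These passages show that expectation is plausible, not that treating staff rate. This also stands.
- **Ready-made recordings.** A reader might infer that suitable recordings already exist in storage. Captured audio is implied, but retention is not stated.
- **Irreversible bias.** If audio is kept, masked rating can be done even after the last visit. It is lost only where the audio is not kept.
- **Importance.** The measure is in neither the hypothesis nor the stated analysis, and the study calls itself a pilot. The illustration assumes a test that the plan does not contain. This limits the weight of the point.

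The objection does not remove the mismatch between the two ratings. Followed as written, the plan pairs a chart score made before treatment, outside any study procedure, with a research-visit score. Stating the missing follow-up details alone would not make the two comparable.

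**Conclusion.** The point holds as a weakness in a subsidiary outcome. The planned before-after perceptual comparison uses a usual-care baseline score made at a known pre-treatment time and a follow-up score whose rater, scale, mode and masking are not specified. In a one-group study by the developers of the mask, it is open to rater expectation and to differences between chart and research raters.

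The documents do not allow the size of any bias to be estimated. On the assumed shifts of 0.10 to 0.50 SD, false-positive rates would run from 7% to 56% at n = 20 and from 8% to 75% at n = 30, against a nominal 5%.

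A reader might go further and conclude that the study's efficacy result is compromised. The documents do not support that: the one stated test is on VHI-10, a patient-reported score that masked listening neither protects nor changes. The consequence is confined to how far the perceptual result can be relied on as corroboration.

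**What to change.** In Research Activities, item 1, state that:

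1. The study's perceptual outcome will be rated from the baseline and follow-up audio of the standard sentence captured for acoustic analysis.
2. The audio will be retained for this purpose. Add this to the Electronic Data Management section, which does not describe audio storage.
3. Date and visit labels will be removed and all samples placed in one random order.
4. A speech-language pathologist already participating in the study, who did not treat that participant, will rate the samples on one named scale.
5. The chart rating will be kept for description only.
6. Participants without a retained baseline sample will be reported as missing for this outcome.

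Any bias figures should be presented only as an assumed illustration.

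The cost is about 1 to 2 hours of existing staff time and a short text change. No extra staff or visit is needed, and clinical care does not change. The downsides are that some baseline samples may be unavailable and that masked scores may look less favourable. Masked rating deals with rater expectation and rater differences only. It does not supply the missing control group, so change from other causes would remain in the comparison.

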*** Provide a justification and describe the qualifications of the individuals who will obtain consent:**

For this project, the PI and the Co-investigators have appropriate expertise and experience to enable them to appropriately discuss the study with participants and obtain consent.

Consent Forms

1. Consent Forms:

Document	Category	Date Modified	Document History
View Facemask consent PittPRO conv 2019.docx(0.03)	Consent Form	2/8/2019	History

Refer to the following templates and instructional documents:

- Guidance - Consent Wording
- Template - Consent Document - Short Form
- HRP-090 - SOP - Informed Consent Process for Research
- HRP-091 - SOP - Written Documentation of Consent

Medical Records

1. You are required to submit this study to the Research Informatics Office, Health Record Research Request (R3). Per UPMC Policy HS-RS0005, all research projects that access or involve UPMC electronic protected health information (e-PHI) must be submitted to R3, with the exception of clinical trials that are contracted through the UPMC Office of Sponsored Programs and Research Support (OSPARS).

Complete the R3 intake form available at <http://rio.pitt.edu/services>. An R3 representative will conduct a review. You will be notified once your R3 review is complete or if anything further is needed.

*** Describe the protected health information that will be collected from the covered entity and/or the research derived information that will be placed into the medical records:**

Medical record information to be accessed for research purposes may include the information associated with the eligibility of subjects as well as their follow up visit information. This would include VHI-10 score, computerized voice testing as well as the clinical examination performed by the laryngologist at any time.

Electronic Data Management

* **Will only anonymous data be collected** (select **NO** if identifiers will be recorded at anytime during the conduct of the study)?

Yes No

Select **all identifiers** to be collected during any phase of the research including screening:

Name:		Internet Protocol (IP) Address:	
E-mail address:		Web Universal Resource Locators (URLs):	
Social security #:		Social security # (for Vincent payment only):	
Phone/Fax #:		Full face photo images or comparable images:	
Account #:		Health plan beneficiary #:	
Medical record #:		Device identifiers/serial numbers:	
Certificate/license #:		Vehicle identifiers/serial #/license plate #:	
		Biometric identifiers, finger and voice prints:	

a: Will you be collecting any of the following **location data**: geographic subdivisions smaller than a State such as street address, city, county, precinct, zip, geocodes, etc.? Yes No

* b: Will you be collecting any **date information** such as birth date, death, admission, discharge, date of surgery/service? Yes No

c: List any other unique identifying numbers, characteristics or codes related to an individual that are to be collected:

d: Will you be collecting any data subject to the General Data Protection Regulation (GDPR)? Yes No

SS# is only being collected as part of the Vincent payment system. This information will be stored in locked file cabinets within the locked offices of the department of Otolaryngology. Only staff involved in the payment process will have access to this information.

* e: Provide a justification for recording Social Security numbers including why it's required, where it's stored, how it's protected and who will have access:

For ALL identifiable data collected, will you be coding the data by Yes No

* removing the identifiers and assigning a unique study ID/code to protect the identity of the participant?

* Will the data be HIPAA de-identified? Yes No

Briefly describe your plan to store coded data separately from the identifiable data:

Electronically stored information will be de-identified and stored using study IDs. The linkage information will be stored in a separate restricted access folder behind the UPMC firewall.

2. * Will sensitive data be collected (e.g., protected health information, mental health, medications, drug/alcohol use, illegal behaviors)? Yes No

3. * Select all locations where data will be stored or accessed (including e.g., personal / employer laptop or desktop):

Storage Device	Description	Identifiable Data	Sensitive Data	De-Identified/Anonymous Data
<small>View</small>	UPMC owned desktop, laptop or other device	no	no	no
<small>View</small>	Server: UPMC Managed Server	yes	yes	yes

4. * Select all technologies being used to collect data or interact with subjects:
N/A

Data Safety and Monitoring

- 1. * Describe your plan to periodically evaluate the data collected regarding both harms and benefits to determine whether subjects remain safe. The plan might include establishing a data monitoring committee and a plan for reporting data monitoring committee findings to the IRB and the sponsor:**

The data and safety monitoring plan for this study will involve quarterly meetings with the PI, Co-Investigators and the staff involved to discuss: the integrity and confidentiality issues, to monitor data collection and recruitment, and to ensure compliance with protocol procedures. A review of research study procedures designed to protect the privacy of the research subjects and the confidentiality of their research data will be discussed. All breaches of confidentiality will be promptly reported to the IRB as well as the Pitt HELP desk. In addition, any unauthorized access to medical record information or unanticipated problems shall be reported to the IRB. A report will be submitted during the course of the IRB renewal of the study.

- 2. * Describe your plan for sharing data and/or specimens:**

This sharing will only occur once the appropriate agreements are executed if deemed appropriate by the Office of Research.

Individuals from both Emory University and Bloomsburg University may be involved in the overall conduct of this study. Information shared with Emory and Bloomsburg University will be shared in a de-identified manner.

- 3. If any research data is collected, stored, or shared in a paper format, address what precautions will be used to maintain the confidentiality of the data:**

Confidentiality will be maintained as per the usual methods in the Dept. of Otolaryngology. Any paper documentation will be maintained in locked file cabinets within the locked offices of the Department of Otolaryngology.

Risk and Benefits

1. * Enter all reasonably foreseeable risks, discomforts, hazards, or inconveniences to the subjects related to subjects' participation in the research:

View	Research Activity	medical record review
	Common Risks	No Value Entered
	Infrequent Risks	No Value Entered
	Other Risks	rare risk of breach of confidentiality

View	Research Activity	wearing partially occluded mask
	Common Risks	No Value Entered
	Infrequent Risks	No Value Entered
	Other Risks	-emotional discomfort/uncomfortable feeling (as stated in consent) -potential for skin irritation due to allergy or mild contact pressure

View	Research Activity	voice therapy session
	Common Risks	No Value Entered
	Infrequent Risks	No Value Entered
	Other Risks	rare risk of worsening voice problem

2. * Describe the steps that will be taken to prevent or to minimize risks:

Confidentiality will be maintained as per the usual methods in the Dept. of Otolaryngology. All electronic subject information will be stored on password protected, restricted access servers. Any paper documentation will be maintained in locked file cabinets within the locked offices of the Department of Otolaryngology.

Though uncommon, it is possible that a patient participant's voice could worsen during a voice therapy session. If this occurs, the voice therapist will give the participant the option of discontinuing voice therapy and can refer the patient back to the treating otolaryngologist for repeat vocal fold examination if so desired.

Wearing of the partially occluded mask could potentially be uncomfortable, emotionally for some individuals. The mask is not "fixed" to the individual's face, and can be removed by the subject at any time. The subject is in control of holding the mask over their nose and mouth. In the event of skin allergy/irritation, mask use may need to be discontinued.

3. Financial risks - will the subject or insurer be charged for any research required procedures?

Yes No

4. Describe the steps that will be taken to protect subjects' privacy:

All study related procedures will be performed in private rooms as is typical of the usual clinical care associated with the diagnosis and treatment of the qualifying voice disorders. Information being collected will be limited to the minimum necessary to achieve the specific aims in this study and to lay the groundwork for future research in this area.

5. What steps will be taken in the event that a clinically significant, unexpected disease or condition is identified during the conduct of the study:

All participants will be under the clinical care of physicians in the Department of Otolaryngology. Usual clinical practice procedures will be maintained.

6. Describe the potential benefit that individual subjects may experience from taking part in the research or indicate if there is no direct benefit. Do not include benefits to society or others:

Subjects may actually receive direct benefit in the form of a more rapid recovery from their voice disorder than may have been received by completing more traditional voice therapy. It is our hypothesis that all subjects will benefit in this way.

7. Do you anticipate any circumstances under which subjects might be withdrawn from the research without their consent?

Yes No

